## **3. STUDY DESIGN**

This bi-center study (MUW, Charité Berlin) is an investigator-driven pilot trial designed to assess the safety, tolerability, pharmacokinetics, pharmacodynamics and efficacy (preliminary assessment) of humanized anti-IL-6 monoclonal antibody clazakizumab in kidney transplant recipients with late ABMR. This study, a phase 2 trial, has two subsequent sub-parts, a randomized placebo-controlled trial (part A) of 12 weeks, where recipients are allocated to receive either clazakizumab (n=10) or placebo (n=10), followed by an open-label prospective study, where all 20 study patients will receive clazakizumab for a period of 40

weeks. In this second part, treatment will be offered to all subjects for two major reasons: (i) in a recent uncontrolled preliminary observational study, interference with IL-6/IL-6R blockade in ABMR patients using tocilizumab was reported to be safe and well tolerated, and first results have suggested stabilization of kidney function in many of the treated patients; (ii) two subsequent protocol biopsies planned in our trial, which are necessary for an in-depth analysis of the early and late effects of IL-6 blockade, would not be justified for long-term placebo treatment. After completion of part A, the randomization sequence will be unblinded for a first analysis of data. A simplified flow chart of the trial is shown in Figure 1:

Figure 1. Trial overview

**Part A:** Patients will be randomized to receive either clazakizumab (25 mg subcutaneous [SC] administration) or placebo (1:1 randomization) for a period of 12 weeks (administration of clazakizumab/placebo at day 0, and after 4 and 8 weeks). After 12 weeks, patients will be subjected to a first follow-up biopsy. Primary goals of this part of the trial are to assess the safety, pharmacokinetics and pharmacodynamics of a short course of treatment. Moreover, part A will allow for a first preliminary assessment of the impact of clazakizumab on ABMR-associated inflammation detected in peripheral blood and in the rejecting organ allograft, on the pharmacokinetics of pantoprazole as a probe drug to investigate influence of IL-6 blockade on cytochrome P450-dependent drug metabolism, and on the short-term course of DSA MFI and kidney allograft function (eGFR, urinary protein excretion). The randomization

sequence will be unblinded for a first data analysis after the last patient has completed the 12-week follow-up period.

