## 7. SAMPLE SIZE AND STATISTICAL ANALYSIS

For this pilot study, no exact sample size estimation can be performed, because the effect size is unknown (there is no prior information to base a sample size on). The primary endpoint will be safety and tolerability. A preliminary assessment of efficacy outcomes in 20

kidney transplant recipients with late ABMR will provide first data on the effect of clazakizumab on clinical, morphological, immunological and molecular endpoints. The respective results (e.g. comparison between clazakizumab and placebo with respect to microcirculation inflammation and molecular rejection scores; course of chronic injury from 3 to 12 months), including an assessment of variability, can be expected to provide a valuable foundation of the design of future trials. Analyses will be conducted according to the intention-to-treat principle. Continuous data (e.g. group comparisons in part A for DSA-MFI, g+ptc score, IF/TA score, molecular ABMR score, eGFR and protein/creatinine ratio after 3 months) will be analysed using parametric and non-parametric (independent/dependent data) tests. These include the Mann Whitney U test or the t-test, as appropriate. Nominal data (e.g. occurrence of AEs in the two treatment groups in part A of the study) will be compared using the Fisher's exact test, when appropriate. Transplant and patient survival or AE (SAE)-free survival will be evaluated using Kaplan Meier analysis and the log rank test will be applied for group comparisons. For paired data (e.g. difference in IF/TA score between month 3 and month 12 in the overall cohort - part B), paired t test or Wilcoxon test will be used as appropriate. Analysis of pharmacokinetics of clazakizumab and pantoprazol will include a description of the time evolution of antibody/drug concentration. Elimination half-life, Tmax, Cmax, clearance and volume of distribution will be computed using standard software. For some study endpoints, data on variability and center (median) that can be expected also for the present study, are available from a recent interventional randomized controlled trial performed at our unit, which included a similar cohort of kidney transplant recipients diagnosed with late ABMR (BORTEJECT, NCT01873157; unpublished data; protocol described in: Eskandary et al., *Trials*. 2014 Apr 3;15:107). The respective data obtained in study groups are listed in the table below:

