## 8. INTERIM ANALYSES

This study will be monitored by an independent data and safety monitoring board (DSMB) to assess the safety and data quality. To timely detect major differences between groups in terms of safety aspects, the board members will be instructed to perform interim analyses after 10 and 20 patients have finalized part A of the study. The DSMB will analyze recorded AEs and safety lab results in relation to the randomization sequence. The trial will be terminated prematurely in the following cases: (i) if adverse events occur which are so serious that the risk-benefit ratio is not acceptable, and (ii) if the number of dropouts is so high that proper completion of the trial cannot realistically be expected. For this pilot trial, exact statistical definitions of criteria for premature study termination are not defined.

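### The randomised safety comparison is planned as two low-power tests (Fisher and log-rank, 10 versus 10) with no interval estimates, so a non-significant result could be misread as evidence of safety

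*Combined protocol and SAP*

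**What the plan says.** Section 7 states: "The primary endpoint will be safety and tolerability". The randomised evidence on it comes from "a randomized placebo-controlled trial (part A) of 12 weeks", in which "recipients are allocated to receive either clazakizumab (n=10) or placebo (n=10").

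The plan compares the arms on safety in three places:
- Section 7, nominal data: "occurrence of AEs in the two treatment groups in part A of the study) will be compared using the Fisher's exact test", qualified by a phrase limiting it to where it is appropriate.
- Section 7, time to event: "AE (SAE)-free survival will be evaluated using Kaplan Meier analysis and the log rank test will be applied for group comparisons".
- Section 8, at the reviews after 10 and 20 patients have finished part A: "The DSMB will analyze recorded AEs and safety lab results in relation to the randomization sequence".

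On size, Section 7 says: "For this pilot study, no exact sample size estimation can be performed, because the effect size is unknown". On stopping, Section 8 says: "For this pilot trial, exact statistical definitions of criteria for premature study termination are not defined".

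Neither section names a significance level, a safety margin, a confidence interval for an AE rate or a risk difference, or a way to interpret a non-significant safety comparison.

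**The concern.** A pilot with safety as its primary endpoint should be able to say how large an excess of harm its data leave open. A p-value from 10 versus 10 does not say that; an interval does.

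Section 2 hypothesises that the drug will be as well tolerated in transplant recipients as IL-6 blockade has been elsewhere. A non-significant Fisher or log-rank result could seem to confirm this even though a large excess remains compatible with the data. The gap matters more because Section 9 says there are no earlier data for this drug in transplant patients on dual or triple immunosuppression. Section 7 also says the trial should inform the design of later trials, and for safety that requires rates with their precision.

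**Working it through.** The plan states no power or significance level, so there is no figure of its own to reproduce. Two-sided 0.05 is assumed.

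**Inputs.** 10 versus 10 patients over 12 weeks (Section 3). From Table 5, placebo versus clazakizumab 25 mg: any AE 60.7% versus 84.7% (rheumatoid arthritis, RA) and 65.9% versus 73.2% (psoriatic arthritis, PsA); SAEs 3.3% versus 8.5% (RA).

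**1. What Fisher's test needs at 10 versus 10.**

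| Placebo events | Fewest clazakizumab events with p ≤ 0.05 | One event fewer |
|---|---|---|
| 0 | 5 (p = 0.033) | 4 (p = 0.087) |
| 1 | 7 (p = 0.020) | 6 (p = 0.057) |
| 2 | 8 (p = 0.023) | 7 (p = 0.070) |
| 5 | 10 (p = 0.033) | 9 (p = 0.141) |
| 6 or more | none | – |

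For 10 versus 6, p = 2 × C(10,6)/C(20,16) = 2 × 210/4845 = 0.087. The chance of six or more placebo patients having an AE is P(Bin(10, 0.607) ≥ 6) = 65% at the RA rate and 77% at the PsA rate of 0.659. In those cases no excess on clazakizumab can reach significance.

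**2. Power.** Fisher power is the sum of the binomial probabilities over all 11 × 11 outcomes with p ≤ 0.05. Log-rank power is from 20,000 simulated trials with exponential times, censoring at 12 weeks and no dropout.

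| Placebo vs clazakizumab | Fisher | Log-rank |
|---|---|---|
| Any AE, RA: 60.7% vs 84.7% | 8.7% | about 27% |
| Any AE, PsA: 65.9% vs 73.2% | 1.7% | about 8% |
| SAE, RA: 3.3% vs 8.5% | 0.06% | about 0.6% |
| Illustrative: 10% vs 30% | 5.7% | about 16% |
| Illustrative: 10% vs 50% | 29.5% | about 52% |

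Check on the first log-rank figure (Schoenfeld): hazard ratio = ln(1 − 0.847)/ln(1 − 0.607) = 2.01; expected events = 10 × (0.607 + 0.847) = 14.54; power = Φ(√14.54/2 × ln 2.01 − 1.96) = Φ(−0.63) = 26.5%.

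Fisher reaches 80% power only when the clazakizumab rate is about 58% against 0% on placebo, or about 78% against 10%.

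**3. What intervals would show.** Take 4/10 on clazakizumab and 1/10 on placebo. Fisher gives p = 0.30. The Wilson limits are 0.168 to 0.687 and 0.018 to 0.404, so the Newcombe interval for the difference of 0.30 is:
- lower: 0.30 − √((0.4 − 0.168)² + (0.404 − 0.1)²) = −0.08
- upper: 0.30 + √((0.687 − 0.4)² + (0.1 − 0.018)²) = 0.60

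That is +30 points, 95% CI −8 to +60. The p-value alone conceals that an excess of 60 points is not excluded.

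For zero events, the exact two-sided 95% upper limit is 1 − 0.025^(1/n): 1 − 0.025^(1/10) = 30.8% and 1 − 0.025^(1/20) = 16.8%.

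**The case against.** The strongest reply is that this is a declared pilot. It claims no power, rests no decision rule on the Fisher p-value, leaves stopping to a risk-benefit judgement, and speaks of preliminary results. Low power is then expected, and intervals could be added at reporting from data already collected. The first part stands: this is no criticism of the sample size. The second shows that the remedy is cheap, not that it is unnecessary. Naming the main safety analysis in advance settles how the primary endpoint will be judged.

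Four stronger readings are tempting, and the documents do not support them:
- **Fisher's test is the whole between-arm safety analysis.** It is not. Section 7 adds the log-rank test and Section 8 adds review by allocation. The log-rank test does better than Fisher but remains weak, and neither addition specifies an interval.
- **The investigators will treat non-significance as safety.** No section says so. The risk is one the plan leaves open.
- **The tests cannot detect harm.** Very large excesses are detectable, as the 80% power figures show.
- **The liver-enzyme categories in Table 5 illustrate the planned test.** The plan does not say these categories will be compared by Fisher's test, and Section 10 counts laboratory changes as AEs only if clinically significant or if they alter study drug. They are left out of the case here.

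**Conclusion.** The concern holds as a missing estimation framework for the primary endpoint. Both planned tests have very low power for the differences that the protocol itself tabulates at 25 mg: Fisher 8.7% and log-rank about 27% for any AE at the RA rates, and both below 1% for SAEs. For any AE, Fisher's test would probably be unable to flag any excess, because six or more placebo events are more likely than not at the Table 5 rates.

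The figures assume a two-sided 5% level, arthritis-trial rates carried over to 12 weeks in transplant recipients, constant hazards, no dropout and a log-rank comparison confined to part A (Section 7 does not state its time window). If 12-week rates are lower than in Table 5, the six-event ceiling is reached less often, but the 10% versus 30% row shows that power stays low. The conclusion that intervals are needed does not depend on which rates apply.

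**What to change.** In Section 7, make estimation the main part A safety analysis:
- The documents contain no list of AE classes, so name a short one: any AE, SAEs and infections (Section 9 already calls for close monitoring of infections). For each, report patients with an event, an exact 95% interval per arm, and the risk difference with a small-sample 95% interval such as Newcombe's.
- Keep Fisher and log-rank p-values as descriptive only.
- For all clazakizumab-exposed patients over the full study, report exact intervals and exposure-adjusted rates. Planned exposure differs by original arm: 12 + 40 = 52 weeks versus 40 weeks.
- State that absence of significance is not evidence of safety, and that zero events leaves 95% upper limits of 31% (0/10) and 17% (0/20). Note that the second figure pools patients with unequal exposure.

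No change is needed to sample size, randomisation, data collection or clinical management. The cost is a paragraph of analysis text, a few lines of code and a more cautious safety statement.

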**Part B:** After 12 weeks, all study patients will enter an open-label part of the study. All 20 subjects will receive clazakizumab (25 mg SC injection) in 4-weekly intervals until the end-of-study (EOS) visit after 52 weeks and will then be subjected to a second protocol biopsy. Major goals of part B are to evaluate the safety and tolerability of a prolonged period of treatment with clazakizumab and the long-term impact of this antibody on the evolution of ABMR, rejection-associated biomarkers and kidney allograft function and survival over a period of 12 months.

We expect a recruitment phase of 18 months, and thus completion of the trial after 30 months.

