Primary outcome measures are the safety and tolerability of clazakizumab, evaluated throughout the study period (19 visits until EOS visit at 52 weeks). Secondary endpoints are pharmacokinetics (clazakizumab concentration) and pharmacodynamics (suppression of CRP). For preliminary efficacy assessment, blood-derived biomarkers of ABMR (HLA/DSA antibody levels, cytokines and markers of endothelial injury, patterns of peripheral blood leukocyte subpopulations) and IL-6/IL-6R gene expression will be assessed at day 0, and after 12 and 52 weeks. The study will include two protocol biopsies, an early biopsy after 11 weeks (end of part A) to primarily dissect the effect of IL-6 blockade on microcirculation inflammation in direct comparison to placebo, and a late biopsy after 51 weeks to assess the

effect of clazakizumab on the progression of chronic injury (cg score, IFTA score). All biopsies will in addition be evaluated for ABMR-typical gene expression patterns (ATAGC, Alberta University, Edmonton; major read-out: molecular ABMR score). We will in addition monitor kidney function, protein excretion and graft survival over the whole study period. Finally, we will assess the impact of IL-6 blockade (as compared to placebo) on pharmacokinetics of pantoprazole reflecting CYP-dependent liver metabolism. At day 0, week 12 and week 52, pantoprazole will be administered at a dosage of 20 mg intravenously, and drug levels will be determined every hour over a period of 6 hours. In patients on continuous proton pump inhibitor therapy, oral treatment will be paused for 3 days before pharmacokinetic testing, and re-started one day thereafter.

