**Collection of biological material (outside routine monitoring).** Plasma (10 mL; cytokines, endothelial markers, TTV load), serum (10 mL; HLA antibodies, cytokines, endothelial markers), whole blood (10 mL; flow cytometry, RNA for gene expression analysis) and urine (10 mL) will be collected before study initiation (day 0), after 12 and after 52 weeks (3x25 mL peripheral blood). For pantoprazole kinetics, peripheral blood samples will be collected serially (6 x 5 mL per day) at day 0, week 12 and week 52, respectively. Finally, for measurement of clazakizumab concentrations and anti-clazakizumab reactivity, serum will be obtained at every study visit (5 mL peripheral blood per visit; total of 17 visits). Biological material will be aliquoted and stored for testing (clazakizumab concentration, anti-clazakizumab antibody detection, HLA antibody detection, detection of cytokines and endothelial markers, TTV quantification) at the Department of Clinical Pharmacology.

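### Section 7 gives no analysis that brings the day-0 pantoprazole curve into the randomised week-12 comparison with placebo

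*Combined protocol and SAP*

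**What the plan says.** Section 5 (text after Table 3) sets the aim: "we will assess the impact of IL-6 blockade (as compared to placebo) on pharmacokinetics of pantoprazole reflecting CYP-dependent liver metabolism". The table of outcomes in the same section lists pantoprazole pharmacokinetics at 0, 12 and 52 weeks among the secondary outcomes.

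The data are well planned. "At day 0, week 12 and week 52, pantoprazole will be administered at a dosage of 20 mg intravenously", with hourly levels over 6 hours, and Section 6 confirms that "peripheral blood samples will be collected serially (6 x 5 mL per day) at day 0, week 12 and week 52". Day 0 precedes any treatment effect, so every patient supplies an individual reference curve.

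The placebo control is short. In part A (Section 3) "recipients are allocated to receive either clazakizumab (n=10) or placebo (n=10"); in part B, "All 20 subjects will receive clazakizumab (25 mg SC injection) in 4-weekly intervals".

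For the analysis, Section 7 has two sentences on this endpoint. The first is "Analysis of pharmacokinetics of clazakizumab and pantoprazol will include a description of the time evolution of antibody/drug concentration". The second is "Elimination half-life, Tmax, Cmax, clearance and volume of distribution will be computed using standard software". The general text of Section 7 on continuous data allows parametric and non-parametric tests for independent or dependent data. It names the Mann-Whitney U test and the t-test, with group comparisons after 3 months as its examples. Its example of paired data is the change in IF/TA score from month 3 to month 12 in the whole cohort.

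**The concern.** An aim stated as a comparison with placebo has no matching contrast, estimate or interval in the analysis section. The pre-treatment curve is collected in all 20 patients but has no stated role in that contrast.

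The two kinds of test that Section 7 names do not fill the gap. An unpaired test on the week-12 value estimates drug versus placebo but ignores day 0. A paired test within one arm uses day 0 but does not estimate drug versus placebo.

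At stake is precision. Section 7 presents the pilot as a source of effect and variability estimates for later trials. With 10 patients per arm, a baseline measurement is one of the few ways to narrow an interval without adding patients.

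**Working it through.** **Stated figure.** There is none to reproduce. Section 7 says that no exact sample size estimation is possible, and Table 4 gives no variability for pantoprazole.

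**Inputs from the documents.** There are 10 patients per arm (Section 3), a pre-treatment test and a week-12 test in each patient (Sections 5 and 6), and no placebo control after week 12 (Section 3, Part B).

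**Assumed inputs.** These are a two-sided 5% level; an SD of log clearance between patients of 0.4, 0.6 or 0.8; a true ratio of 1.5 or 2; and a correlation rho between log day-0 and log week-12 values of 0 to 0.8.

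**Week-12 values alone.** SE = SD × √(2/10), with 18 df. For SD 0.6, SE = 0.6 × 0.447 = 0.268. For a 2-fold effect the noncentrality is ln 2 / 0.268 = 0.693 / 0.268 = 2.58, and power is 69%. The 95% CI factor is exp(2.101 × 0.268) = 1.76, so the ratio is known to within a multiplication or division by 1.76.

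**Adjusted for day 0.** Residual SD = SD × √(1 − rho²) × √(1 + 1/15), with 17 df. The last factor, 1.033, allows for estimating the covariate effect. For SD 0.6 and rho 0.5, residual SD = 0.6 × 0.866 × 1.033 = 0.537, SE = 0.240, power is 78%, and the CI factor is exp(2.110 × 0.240) = 1.66.

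Power in %, by the same formulas:

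| log SD | true ratio | unadjusted | rho 0.3 | rho 0.5 | rho 0.7 | rho 0.8 |
|---|---|---|---|---|---|---|
| 0.6 | 2 | 68.6 | 69.6 | 77.7 | 91.0 | 97.5 |
| 0.6 | 1.5 | 29.8 | 30.4 | 35.7 | 48.9 | 63.3 |
| 0.8 | 2 | 45.0 | 45.8 | 53.3 | 69.7 | 83.8 |
| 0.8 | 1.5 | 18.8 | 19.1 | 22.3 | 30.5 | 40.7 |
| 0.4 | 1.5 | 57.3 | 58.3 | 66.6 | 82.5 | 93.1 |
| 0.4 | 2 | 95.6 | 95.9 | 98.3 | 99.9 | 100.0 |

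For SD 0.6 the CI factor goes from 1.76 unadjusted to 1.75, 1.66, 1.52 and 1.42 at rho 0.3, 0.5, 0.7 and 0.8.

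**Downside.** At rho 0 with SD 0.6 and a 2-fold effect, power falls from 68.6% to 65.5%, about 3 points. Charging one more degree of freedom for the stratum (16 df) changes power by less than 0.5 points in any of these cases.

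**Change score, for comparison.** Its SD is SD × √(2(1 − rho)). At 80% power the unadjusted comparison detects 1.32 SD. A between-arm comparison of changes detects 1.32 × √1.4 = 1.57 SD at rho 0.3, 1.32 SD at rho 0.5 and 0.84 SD at rho 0.8. It helps only if rho exceeds 0.5.

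**The case against.** The strongest reply is that the gap is inferred from silence. Section 7 says what the pharmacokinetic analysis will include, which is not a closed list. The general rule covers independent and dependent data, and its examples are only examples. A t-test or Mann-Whitney test on each patient's change from day 0, compared between arms, would fit that wording and would use the baseline. This stands: a reader might infer that the plan commits the comparison to unadjusted week-12 values, and the text does not support that. What remains is that no such analysis is stated. The choice is not neutral either, since a change score is less precise than the week-12 value alone when rho is below 0.5.

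Second, the size is assumed throughout. That also stands. At rho 0.3 the gain is at most about 1 point, and even at rho 0.5 it is under 5 points in two of the six cases in the table (SD 0.4 with a 2-fold effect, SD 0.8 with a 1.5-fold effect).

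Third, this is a pilot with no power claim, and Section 7 names no baseline covariate for any continuous endpoint. That limits the weight of the point. It does not remove it, because effect estimates and their variability are what the pilot is meant to deliver.

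Two further inferences are tempting and should not be drawn. One is that differences in metaboliser type are the main noise in a week-12 comparison. The documents hold only the title of the cited work on polymorphic enzymes and no data on metaboliser status. That title concerns phenotype shifting with inflammation, which is no evidence for a high day-0 to week-12 correlation. The other is that the gap weakens the co-medication advice under Drug Interaction in Section 9. That advice is general and does not depend on the pantoprazole result.

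**Conclusion.** The point holds as a gap in specification for which a better method is available from data already planned. The promised placebo comparison has no stated analysis that uses the day-0 value, and week 12 is the only time at which the comparison is randomised.

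The benefit ranges from negligible at rho 0.3 to substantial at rho 0.7 or above: for log SD 0.6 and a 2-fold effect, from 69% power to between 70% and 98%. The documents supply neither the SD nor the correlation, so no single figure in that range can be claimed. The downside is small and bounded, at about 3 points of power if day 0 carried no information. The endpoint is secondary, the trial is a pilot, and nothing here shows an error in a stated figure or a conflict with the trial's main safety purpose.

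**What to change.** Add one definition to Section 7: the effect of clazakizumab on pantoprazole is the ratio of geometric mean clearance (or AUC, with one of the two chosen in advance) at week 12, clazakizumab versus placebo. It is estimated from a linear model on log values, with the log day-0 value and the ABMR-type randomisation stratum (Section 3, Random allocation) as covariates, and reported with a 95% CI.

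State that any week-52 comparison, or a mixed model over all three tests, is descriptive, because week 52 has no placebo control.

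The cost is this wording and two degrees of freedom. No sample, visit or patient is added, and no clinical procedure changes.
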